7.5. Preparation/Handling/Storage/Accountability

LY2606368 will be administered as an IV infusion using a central or peripheral IV line and will be filtered through an in-line filter. LY2606368 should be handled according to standard procedures and precautions consistent with a cytotoxic anticancer drug. For the most current detailed formulation information and preparation instructions, refer to the IB and Pharmacy Binder.

7.5.1. LY2606368 Mesylate Monohydrate

The LY2606368 mesylate monohydrate drug product contains 40 mg/vial of the base compound LY2606368. The vial contains a 3% excess to facilitate the withdrawal of the label amount 40 mg/vial for use with an appropriate device, such as an infusion set. The drug product is stable when stored at room temperature.

Reconstituting the vial contents with 19 mL of water for injection yields a clear yellow solution with a concentration of 2 mg/mL of LY2606368 and an osmotic pressure ratio of 344 mOsm. The reconstituted formulation is stable for at least 24 hours at room temperature; however, since the reconstituted drug product does not contain a preservative, the unused solution must be discarded after 12 hours. The reconstituted solution may be diluted with dextrose 5% injection (D5W) prior to administration. LY2606368 is incompatible with solutions containing saline or lactated Ringer's and must **NOT** be mixed or administered simultaneously with other drugs through the same infusion line. The infusion line should be flushed with D5W before and after LY2606368 administration.

7.5.2. LY2606368 Lactate Monohydrate

A 67-mg strength of LY2606368 lactate monohydrate drug product is in development and may be used in Study JTJH. The vial will contain a slight excess to facilitate the withdrawal of the label amount 67 mg/vial for use with an appropriate device, such as an infusion set.

Reconstituting the vial contents with water for injection yields a clear yellow solution with a concentration of 3.35 mg/mL of LY2606368. For the most current detailed information on this strength refer to the IB and Pharmacy Binder.

7.6. Treatment Compliance

The study medication will be administered only at the investigational sites by the authorized study site personnel. As a result, treatment compliance is ensured.

7.7. Concomitant Therapy

No other chemotherapy, immunotherapy, cancer-related hormone therapy, herbal drugs intended to treat cancer, or experimental drugs will be permitted while the patients are on this study. Radiotherapy (including palliative radiotherapy) will only be permitted if it is agreed upon by the both investigator and Lilly. If the lesion that is to be treated is a target lesion, the lesion will be censored at the time of treatment. However, the patient may be eligible to remain on study drug treatment provided there are other lesions that can be followed for progression. Treatment delays of LY2606368 may be required if radiotherapy is administered. In addition, any disease progression requiring other forms of specific antitumor therapy will also necessitate early discontinuation from the study. Replacement hormonal therapy initiated before study entry will be allowed.

Patients should receive full supportive care during the trial. American Society of Clinical Oncology (ASCO) guidelines (Smith et al. 2015) should be followed for patients requiring support with granulocyte-colony stimulating factor (G-CSF). Primary or secondary prophylactic G-CSF support is permitted at the discretion of the investigator. Per the National Comprehensive Cancer Network (NCCN) guidelines, Phase 2 data support the use of pegfilgrastim in regimens with a 2-week cycle, and there is uniform consensus that this is appropriate (Category 2A) (NCCN guidelines for myeloid growth factors [WWW]). As a result, filgrastim, filgrastim biosimilars, or pegfilgrastim may be used.

Prophylactic antibiotics should be considered for use in patients that have experienced neutropenic fever or patients deemed at higher risk for neutropenic fever by the investigators. The treatment should be consistent with ASCO guidelines (Flowers et al. 2013).

Transfusion of packed red blood cells (RBCs) within 14 days of study entry is not permitted. The initiation of erythropoietin therapy to meet eligibility criteria is not permitted. Patients who are stable on erythropoietin for >1 month before study entry may continue their treatment. Erythropoietin and packed RBC transfusion may be used according to ASCO guidelines (Rizzo et al. 2008) if clinically indicated at any time during the study.

In Study JTJA, no prolongations in average QTcF interval (Fridericia's formula) >480 msec or of ≥ 60 msec from baseline were observed with LY2606368 monotherapy (n=101) at any time point. A thorough corrected QT (QTc) study has not yet been conducted. On days when LY2606368 is administered, patients should avoid taking multiple concomitant medications that are known or suspected to cause prolonged QTc or Torsades de Points and, if possible, alternative agents should be considered.

[figure not shown]

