Relative day within a cycle		Period begins the day after stopping of study treatment and lasts approximately 30 days	Period begins 1 day after short-term follow-up period is completed and continues until death, study withdrawal, or the patient is lost to follow-up	
Procedure Category	Procedure			Comments
Physical Examination	Physical examination (including weight)	X		
	Vital signs	X		Includes blood pressure, pulse, and temperature.
	ECOG performance status	X		
Tumor Assessment	Radiologic imaging according to RECIST 1.1	X		The same method of imaging (CT scan, spiral CT, etc.) used at baseline should be used for each subsequent assessment. Not required if progressive disease is documented while on treatment or if there are clear signs of clinical progression.
	Tumor measurement (palpable or visible)	X		Performed at the same time as radiologic imaging.
Adverse Events Collection/CTCAE Grading		X	X	After Visit 801, only study treatment-related serious events are reported.
Concomitant Medication Notation		X		
Lab/Diagnostic Tests	Hematology	X		
	Chemistry	X		
	ECG	X		
	Exploratory blood sample for biomarkers	X		
	Plasma biomarker sample	X		
	Optional posttreatment biopsy		X	
Health Outcome Measure	Lung Cancer Symptom Scale	X		The LCSS will need to be administered prior to extensive interaction with site personnel.
Follow-Up	Survival Assessment		X	Approximately every 60 (±14) days (telephone assessment is acceptable).

Abbreviations: CT = computed tomography; CTCAE = Common Terminology Criteria for Adverse Events (NCI 2009); ECOG = Eastern Cooperative Oncology Group (Oken et al. 1982); LCSS = Lung Cancer Symptom Scale; RECIST 1.1 = Response Criteria In Solid Tumors Version 1.1 (Eisenhauer et al. 2009).

Table JTJH.2.4. Continued Access Schedule of Activities

	Study Treatment	Follow-Up ^a	
Visit	501-5XX	901	
Procedure ^b			Comments
AE collection	X	X	
Administer LY2606368	X		IV over approximately 60 (+10) minutes once every 14 days.

Abbreviations: AE = adverse event; IV = intravenously.

- a Continued access follow-up begins 1 day after the patient and the investigator agree that the patient will no longer continue treatment in the continued access period and lasts approximately 30 days. No follow-up procedures will be performed for a patient who withdraws informed consent unless he or she has explicitly provided permission and consent.
- b Efficacy assessments will be done at the investigator's discretion based on the standard of care.

3. Introduction

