8.1. Discontinuation from Study Treatment

Patients will be discontinued from study treatment in the following circumstances:

- the patient is enrolled in any other clinical trial involving an investigational product or any other type of medical research judged not to be scientifically or medically compatible with this study
- the patient becomes pregnant during the study
- the patient is significantly noncompliant with study procedures and/or treatment
- the patient has evidence of progressive disease
- the patient experiences unacceptable toxicity
- the patient, for any reason, requires treatment with another therapeutic agent that has been demonstrated to be effective for treatment of the study indication. Discontinuation from study treatment will occur prior to introduction of the new agent.
- the investigator decides that the patient should be discontinued from LY2606368
- the patient requests to be discontinued from LY2606368

Patients who are discontinued from LY2606368 will have follow-up procedures performed as shown in the Schedule of Activities (Section 2).

8.1.1. *Discontinuation of Inadvertently Enrolled Patients*

If Lilly or the investigator identifies a patient who did not meet enrollment criteria and was inadvertently enrolled, a discussion must occur between the Lilly CRP and the investigator to determine if the patient may continue in the study. If both agree it is medically appropriate to continue, the investigator must obtain documented approval from the Lilly CRP to allow the inadvertently enrolled patient to continue in the study with or without LY2606368.

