8.2. Discontinuation from the Study

Patients will be discontinued from the study in the following circumstances:

- participation in the study needs to be stopped for medical, safety, regulatory, or other reasons consistent with applicable laws, regulations, and good clinical practice (GCP)
- the investigator decides that the patient should be discontinued from the study
- the patient requests to be discontinued from the study

Patients who discontinue from the study early will have end-of-study procedures performed as shown in the Schedule of Activities (Section 2).

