10.3.3.4. Poststudy-Treatment-Discontinuation Therapy

The numbers and percentages of patients receiving post study-treatment-discontinuation anticancer therapies will be provided by type of therapy (surgery, radiotherapy, or systemic therapy), and by drug class and/or name, overall and by line of therapy.

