5.3. Handling of Dropouts or Missing Data

The full analysis set, which includes all enrolled patients, will be used for all baseline, efficacy, health outcomes, dosing/exposure, and safety analyses.

Baseline will refer to the last non-missing observation prior to first administration of any treatment unless stated otherwise. Missing data, except for dates, will not be imputed. When dates are used in calculations, missing days will be replaced with 15th of the month and missing day/month with 01 JULY. Where windows are allowed for data collection and there is more than one reading in any window, appropriate consideration will be given as to whether only one value from the window should be used, and if so how it should be chosen. This could either be the mean (geometric mean) or the value closest to the mid-point of the window or the value closest to the data collection time of another variable if the analysis involves time-matched analyses.

If a patient discontinues from study treatment for any reason other than becoming lost to follow-up or death, regular follow-up visits will be conducted to collect information on subsequent non-protocol defined therapy, first disease recurrence, and death. Therefore, it is possible to obtain information for time-to-event endpoints for these patients.

In the primary efficacy analysis, a patient with a tumor response of “not evaluable” will be included in the denominator for the purpose of calculating ORR.

In the health outcomes/quality-of-life analyses, if any of the 6 symptom-specific questions have not been completed, the ASBI will not be calculated. Similarly, if any of the 9 LCSS questions have not been completed, the total LCSS score will not be calculated.

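### Protocol 7.7 takes patients who progress and need other therapy off the study, against 8.1, 8.2 and the follow-up schedule; separately, later therapy and first recurrence are not scheduled after Visit 801

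*Protocol*

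**What the plan says.** **Leaving the study or stopping treatment**

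- Protocol 7.7 (Concomitant Therapy): "any disease progression requiring other forms of specific antitumor therapy will also necessitate early discontinuation from the study".
- Protocol 8.1 lists, among the reasons to stop study treatment, that "the patient has evidence of progressive disease". It also lists the need for another agent effective in this disease, adding: "Discontinuation from study treatment will occur prior to introduction of the new agent". It then says: "Patients who are discontinued from LY2606368 will have follow-up procedures performed as shown in the Schedule of Activities".
- Protocol 8.2 opens with "Patients will be discontinued from the study in the following circumstances". It gives three reasons: medical, safety, regulatory or similar grounds; the investigator's decision; and the patient's request. Neither progression nor new therapy is among them.

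**Follow-up after treatment**

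- In Protocol Table JTJH.2.3, long-term follow-up (Visits 802-X) "continues until death, study withdrawal, or the patient is lost to follow-up". Its column holds a survival assessment about every 60 (±14) days (telephone allowed), treatment-related serious events and an optional biopsy. Imaging and concomitant medication are marked at Visit 801 only, about 30 days after treatment stops.
- SAP 5.3 says of patients who stop treatment for any reason except death or loss to follow-up: "regular follow-up visits will be conducted to collect information on subsequent non-protocol defined therapy, first disease recurrence, and death". It infers that time-to-event information can be obtained for them.
- Protocol 10.3.3.4: "The numbers and percentages of patients receiving post study-treatment-discontinuation anticancer therapies will be provided by type of therapy", and also by drug class or name and by line of therapy.

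**The concern.** There are two separate problems.

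First, 7.7 gives a consequence for progression that the discontinuation sections do not. Long-term follow-up stops at study withdrawal, so a site could read 7.7 as grounds to end survival contacts once a patient progresses and moves to another drug. Protocol 10.3.1 and SAP 5.10.2 censor OS at the last date known alive, which would then fall near progression. Censoring at that moment depends on prognosis: progression raises the risk of death, and being fit enough for more therapy lowers it. Kaplan-Meier assumes neither kind of dependence. The study has no concurrent control, so a distorted OS curve has no comparator within the trial to expose it.

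Second, whatever sites make of 7.7, the SAP and Protocol 10.3.3.4 count on data that the schedule does not provide for. The later-therapy summary is needed to interpret OS. First recurrence matters for progression-free survival (PFS) and duration of response in patients who stop treatment before progressing.

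**Working it through.** The plan gives no figure on this point, so the check is mainly a comparison of passages. A conditional illustration of size follows.

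**1. Progression that needs other therapy**

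| Place | Consequence |
|---|---|
| Protocol 7.7 | Leaves the study |
| Protocol 8.1 | Stops study treatment; follow-up per Section 2 |
| Protocol 8.2 | Not a reason to leave the study |
| Table JTJH.2.3 | Survival contacts go on until death, withdrawal or loss |
| SAP 5.3 | Follow-up continues and records later therapy |

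Section 7.7 stands alone against the other four.

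**2. Data relied on and data scheduled after Visit 801**

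| Item | Relied on in | Scheduled in Visits 802-X |
|---|---|---|
| Death | SAP 5.3, OS | Yes, about every 60 days |
| Later anticancer therapy | SAP 5.3, Protocol 10.3.3.4 | No |
| First recurrence | SAP 5.3 | No |

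A patient who stops treatment without progression has one scan at Visit 801 and none scheduled afterwards.

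**3. Size if 7.7 is read literally (illustration only)**

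Inputs:
- 58 patients per cohort (Protocol 5.2).
- Historical topotecan medians of 13.3 weeks to progression and 25.0 weeks for survival (Protocol 3.1). They are used here as the median time to first event and the true median OS.
- Assumed: a share *q* = 0.7 to 0.9 of first events are progressions, and a share *u* = 0.3 or 0.6 of progressing patients need other therapy, with *u* = 1 as the extreme. Times are exponential, need for therapy is unrelated to prognosis after progression, and all other patients are followed to death.

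Formulas:
- First-event hazard λ = ln 2 / 13.3 = 0.0521 per week. Death hazard before progression is λ(1 − *q*).
- Hazard after progression μ is solved from S(25) = 0.5, with S(t) = e^(−λt) + *q*λ(e^(−λt) − e^(−μt))/(μ − λ).
- Share cut at progression = *q* × *u*. Deaths kept = 58 × (1 − *qu*).
- With P0 = e^(−λt) and P1 = (1 − *u*)*q*λ(e^(−λt) − e^(−μt))/(μ − λ), Kaplan-Meier estimates the hazard [λ(1 − *q*)P0 + μP1]/(P0 + P1). Its median is where the cumulative hazard reaches ln 2.

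| *q* | *u* | Share cut | Deaths kept of 58 | Kaplan-Meier median (true 25.0 weeks) |
|---|---|---|---|---|
| 0.7 | 0.3 | 0.21 | 46 | 27.1 |
| 0.8 | 0.3 | 0.24 | 44 | 27.9 |
| 0.9 | 0.3 | 0.27 | 42 | 28.6 |
| 0.7 | 0.6 | 0.42 | 34 | 30.5 |
| 0.8 | 0.6 | 0.48 | 30 | 33.0 |
| 0.9 | 0.6 | 0.54 | 27 | 35.7 |

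At *u* = 0.3 to 0.6 the number cut runs from 0.21 × 58 = 12 to 0.54 × 58 = 31. At *u* = 1 the median is 13.3/(1 − *q*), which is 44 weeks at *q* = 0.7 and longer for larger *q*.

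The upward shift reflects a higher death hazard after progression (0.059 to 0.081 per week) than before it (0.005 to 0.016). If the patients who receive more therapy are the fitter ones, removing them pulls the other way, so the true direction is not known.

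If sites follow Table JTJH.2.3, *u* has no effect and nothing is lost.

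**The case against.** The strongest reply is that 7.7 is a stray phrase in a concomitant-therapy section, and that the governing text is clear. Sections 8.1 and 8.2 deal directly with discontinuation. Section 7.8 keeps all patients on the schedule until study completion. Table JTJH.2.3 waives the Visit 801 scan when progression is already documented, so it expects progressed patients in follow-up, and Section 9.8.2 plans biopsies after progression. The documents also never say that discontinuation under 7.7 is the same as the withdrawal that ends long-term follow-up. All of this stands, and it makes the literal reading a risk rather than the plan's evident intent. It does not remove the risk. The schedule that 7.8 invokes itself ends at study withdrawal, and the survival search in 8.3 covers patients lost to follow-up, not patients taken off the study.

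A reader might go further and infer that the schedule does not collect death, or that OS will be cut at progression. The documents support neither. Survival is assessed about every 60 days, and the loss arises only where a site puts 7.7 above 8.1, 8.2, 7.8 and the schedule.

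Nor can one say that later therapy will go unrecorded. The case report form is not among the documents and may capture it. What can be said is that it is not scheduled.

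On recurrence, SAP Table JTJH.5.2 already gives censoring rules for patients without documented progression. That settles how to analyze the gap; it does not supply the data that SAP 5.3 says will be collected. The group concerned is limited to patients who stop treatment without progression and are still progression-free at the Visit 801 scan. The documents do not give its size.

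**Conclusion.** The point holds as two limited findings.

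- **Contradiction.** Section 7.7 conflicts with 8.1, 8.2 and Table JTJH.2.3, and the passages must be reconciled. If 7.7 is followed literally, and leaving the study counts as study withdrawal, OS follow-up ends around progression with informative censoring. If the schedule is followed, there is no loss. The illustrated shift of the median from 25 to about 27-36 weeks depends on assumed shares and a historical topotecan result. It shows that the literal reading would matter, and it does not predict this trial's result.
- **Collection gap.** Later anticancer therapy and first recurrence are relied on but not scheduled after Visit 801. This affects the later-therapy summary and, for patients who stop without progression, PFS and duration of response.

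The primary overall response rate is unaffected: SAP 5.10.1 takes best response only up to the end of treatment, and 7.7 and 8.1 differ only on what happens after that. OS and PFS are secondary and estimated descriptively. The change is worth making because it costs little, but the design does not depend on it.

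**What to change.** 1. Reconcile the 7.7 phrase with 8.1 and 8.2 so that survival follow-up under Table JTJH.2.3 continues after progression or new therapy. Leave the treatment-stopping rules as they are. Cost: one phrase.
2. Add to the existing Visit 802-X contact the start date and type of each new anticancer therapy, and the date of any radiographic progression seen on locally performed imaging. Cost: one schedule row and one case report form page, with no new visit or scan. This does not replace scheduled scans for PFS or duration of response. PFS needs radiographic documentation, SAP Table JTJH.5.2 excludes symptomatic deterioration, and a telephone call can only report imaging done for other reasons.
3. If the second change is not made, limit the SAP 5.3 statement to death and the Protocol 10.3.3.4 summary to therapy recorded up to Visit 801. Cost: two text edits. If the case report form already collects later therapy, one line in the schedule that says so is enough for that item.

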7.8. Treatment after the End of the Study

Study completion will occur no more than 1 year after the last patient enrolls in the trial, following the final analyses of progression-free survival (PFS) and overall survival (OS). Investigators will continue to follow Schedule of Activities (Section 2) for all patients until notified by Lilly that study completion has occurred.

7.8.1. Continued Access

Patients who are still on LY2606368 at the time of study completion may continue to receive LY2606368 if they are experiencing clinical benefit and no undue risks. The continued access period will apply to this study only if at least 1 patient is still on LY2606368 when study completion occurs. Lilly will notify investigators when the continued access period begins. Lilly may allow patients to enroll in a LY2606368 “rollover” protocol to provide long-term continued access for patients enrolled in this study. The continued access period is shown in Figure JTJH.7.1.

The patient’s continued access to LY2606368 will end when a criterion for discontinuation is met (Section 8). Continued access follow-up will begin the day after the patient and the investigator agree to discontinue LY2606368 and lasts approximately 30 (± 7) days. Follow-up procedures will be performed as shown in the Continued Access Schedule of Activities (Table JTJH.2.4).

^a Lilly will notify sites when the continued access period begins and ends.

^b Final analysis of overall survival. Lilly will notify sites when study completion occurs.

^c End of trial occurs at the last visit or last scheduled procedure for the last patient.

Figure JTJH.7.1. Continued access diagram.

Patients who are in short-term follow-up when the continued access period begins will continue in short-term follow-up until the 30-day short-term follow-up visit is completed. Long-term follow-up does not apply.

Patients who are in long-term follow-up when the continued access period begins will be discontinued from long-term follow-up.

8. Discontinuation Criteria

8.1. Discontinuation from Study Treatment

Patients will be discontinued from study treatment in the following circumstances:

- the patient is enrolled in any other clinical trial involving an investigational product or any other type of medical research judged not to be scientifically or medically compatible with this study
- the patient becomes pregnant during the study
- the patient is significantly noncompliant with study procedures and/or treatment
- the patient has evidence of progressive disease
- the patient experiences unacceptable toxicity
- the patient, for any reason, requires treatment with another therapeutic agent that has been demonstrated to be effective for treatment of the study indication. Discontinuation from study treatment will occur prior to introduction of the new agent.
- the investigator decides that the patient should be discontinued from LY2606368
- the patient requests to be discontinued from LY2606368

Patients who are discontinued from LY2606368 will have follow-up procedures performed as shown in the Schedule of Activities (Section 2).

8.1.1. *Discontinuation of Inadvertently Enrolled Patients*

If Lilly or the investigator identifies a patient who did not meet enrollment criteria and was inadvertently enrolled, a discussion must occur between the Lilly CRP and the investigator to determine if the patient may continue in the study. If both agree it is medically appropriate to continue, the investigator must obtain documented approval from the Lilly CRP to allow the inadvertently enrolled patient to continue in the study with or without LY2606368.

